## 2 Objectives and endpoints

### 2.1 Objectives

- Constructing a Generative AI-Powered Puncture Surgery Navigation System for lung punctures (GPS-Lung) system for lung puncture.
- Using the GPS-Lung system to guide lung puncture surgery, improving puncture surgery efficiency, reducing radiation exposure and minimizing complications.

## Statistical Analysis Plan

### 2.2 Endpoints

#### 2.2.1 Primary endpoint

Puncture times of participants for GPS-Lung system and CBCT-guided lung puncture procedures.

#### 2.2.2 Second endpoints

Radiation dose, duration of surgery and intraoperative and postoperative complications within 7 days of participants for GPS-Lung system and CBCT-guided lung puncture procedures.

#### 2.2.3 Other endpoints

- Algorithmic performance for image quality.
- Doctors' scoring of image quality and lesion visualization.

## 3 Study Methods

### 3.1 General study design and plan

[figure not shown]
- Study configuration and experimental design: This study is a clinical randomized controlled trial.
- Type of comparison: Puncture times, duration of surgery, radiation dose and complications of participants guided by the GPS-Lung system for PLP versus those guided by conventional CBCT are compared.
- Type of control(s): CBCT-guided PLP without the use of the GPS-Lung system.
- Level and method of blinding: This is a double-blind study (Investigators and participants will be unaware of whether they are randomized to GPS-Lung system guided PLP group or CBCT-guided PLP group without aid of AI).

## Statistical Analysis Plan

- Method of treatment assignment: Participants will be randomly assigned to treatment or control group using a computer-generated random number sequence, with a 1:1 allocation ratio.
- At what point in time subjects are randomized relative to treatments: Participants will be randomized before PLP initiation.

The proposed clinical workflow is present in **Figure 1**

## Statistical Analysis Plan

**Figure 1.** Clinical workflow of this study.

## Statistical Analysis Plan

### 3.2 Inclusion and exclusion criteria

#### Inclusion criteria

- Participants who require CBCT-guided PLP and meet the clinical indications for the procedure.
- Participants with pre-operation CT images available.
- Participants whose physical condition is suitable for PLP.

#### Exclusion criteria

- Participants with a history of allergy or serious adverse reactions to iodine contrast media or other related drugs.
- Participants are pregnant or breastfeeding.
- Participants are unwilling or unable to sign informed consent.

### 3.3 Randomization and binding

Randomization will be performed using a web-based system, employing computer-generated permuted-block sequences with stratification by center. Notably, this centralized, web-based randomization service ensures concealment of trial-group assignments.

A double-blind design will be conducted to ensure that neither participants nor researchers will be aware of group allocation during this study. Participants, researchers, data collectors and outcome assessors will be blinded to group assignment. Statisticians and authors will be also blinded to subgroup allocation during data analysis. Doctors, technicians and trial nurses will be aware of subgroup assignments but will not be involved in data collection or analysis.

### 3.4 Detailed sample size calculation

The randomization process was conducted by an independent statistician who was not involved in the recruitment, treatment, or data analysis of the participants. The sample size was calculated for the primary endpoint (The mean number of intraoperative

## Statistical Analysis Plan

puncture times). A total of 38 participants received CBCT-guided PLP from retrospective cohort were included from Wuhan Union Hospital. The mean (SD) puncture times of these patients were  $2.3 \pm 2.2$ . We used a 2.5% one-sided significance level with 90% efficacy for sample allocation on a 1:1 basis. The sample size was calculated based on the following formula:

$$n = \frac{2(Z_{\alpha/2} + Z_{\beta/2})^2 * \sigma^2}{\Delta^2}$$

$n$  represents the sample size of each group.  $Z_{\alpha/2}$  represents the critical value of the significance level ( $\alpha$ ), and the  $\alpha=0.025$  in the study.  $Z_{\beta/2}$  represents the critical value of efficacy ( $1 - \beta$ ), and the  $\beta=0.9$  in the study.  $\sigma^2$  represents the within-group variance. In the current,  $\sigma$  was substituted by the standard deviation of puncture times from 38 participants.  $\Delta$  represents the smallest difference between the means of the two groups. In the current, the  $\Delta$  was considered as 1. Therefore, the sample size to be included in this study for each group is 103. We will included 220 participants (each group 110 participants) (Figure 2).

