## Study Protocol

level with 90% efficacy for sample allocation on a 1:1 basis. The sample size was calculated based on the following formula:

$$n = \frac{2(Z_{\alpha/2} + Z_{\beta/2})^2 * \sigma^2}{\Delta^2}$$

n represents the sample size of each group.  $Z_{\alpha/2}$  represents the critical value of the significance level ( $\alpha$ ), and the  $\alpha=0.025$  in the study.  $Z_{\beta/2}$  represents the critical value of efficacy (1 -  $\beta$ ), and the  $\beta=0.9$  in the study.  $\sigma^2$  represents the within-group variance. In the current,  $\sigma$  was substituted by the standard deviation of puncture times from 38 participants.  $\Delta$  represents the smallest difference between the means of the two groups. In the current, the  $\Delta$  was considered as 1. Therefore, the sample size to be included in this study for each group is 103. We will included 220 participants (each group 110 participants).

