**Test Direction**

Alternative Hypothesis: One-Sided

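### Does the misprinted sample-size formula undermine the 103 per group or the significance level?

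*SAP*

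**What the plan says.** Protocol section 9 and SAP section 3.4 carry the same account. In words, the SAP states: "We used a 2.5% one-sided significance level with 90% efficacy for sample allocation on a 1:1 basis". Both documents then print a per-group formula, n = 2(Z at alpha/2 + Z at beta/2)² σ² / Δ², and define its terms. Alpha is given as 0.025. Beta is given as 0.9, although the symbol is described as relating to the power. The SD, 2.2, "was substituted by the standard deviation of puncture times from 38 participants", and the difference Δ "was considered as 1. Therefore, the sample size to be included in this study for each group is 103". The Protocol draws the same conclusion: "Therefore, the sample size to be included in this study for each group is 103". Both then round the target up to 110 per group, 220 in all.

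The SAP, but not the Protocol, also reproduces the software settings and output as Figure 2. They show a two-sample equal-variance t-test, with "Alternative Hypothesis: One-Sided", alpha 0.025, power 0.9, difference 1 and SD 2.2. The output is 103 per group with an actual power of 0.90089.

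SAP section 5.5 names the candidate tests for the primary and secondary outcomes (t-test or Mann-Whitney U; chi-squared or Fisher's exact) without giving a significance level or a direction. Protocol section 10 gives neither as well.

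**The concern.** Both documents offer 103 as the consequence of the formula, and it is not. Three things in the notation are wrong. The value 0.9 is the power, so beta should be 0.1. Beta is halved, which has no place in a one-sided comparison for a difference. Alpha is halved although 0.025 is already the one-sided level.

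A wrong formula can hide a wrong sample size, which would be serious. The second worry is the threshold. Halving 0.025 gives 0.0125 in one tail, a critical value of 2.241 instead of 1.960. Because SAP section 5.5 is silent on level and direction, the sample-size section is the only place where the threshold for the primary outcome can be found, and it could be read as giving two. If the stricter one were applied at analysis, the trial would fall short of its stated 90% power.

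**Working it through.** **Inputs** (SAP section 3.4, with the same values in Protocol section 9): σ = 2.2, Δ = 1, one-sided level 0.025, power 0.90, equal allocation. The common factor is 2σ²/Δ² = 2 × 4.84 / 1 = 9.68.

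**Step 1: reproduce the plan's figure.** For an equal-variance t-test with n per group, the noncentrality is Δ / (σ√(2/n)) on 2n − 2 degrees of freedom, tested at one-sided 0.025.

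- n = 102: power 0.8981
- n = 103: power 0.9009, with noncentrality √(103/2)/2.2 = 3.26 on 204 degrees of freedom
- n = 110: power 0.9187

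So 103 is the smallest group size that reaches 90%, and the software's 0.90089 is matched.

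**Step 2: the printed formula under different readings.**

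| Reading | Z values | n = 9.68 × (sum)² | Per group |
|---|---|---|---|
| As printed (alpha/2 = 0.0125, beta/2 = 0.45) | 2.241 + 0.126 | 54.2 | 55 |
| Beta read as 0.1, both halved | 2.241 + 1.645 | 146.2 | 147 |
| Beta 0.1, only alpha halved | 2.241 + 1.282 | 120.1 | 121 |
| Beta 0.1, only beta halved | 1.960 + 1.645 | 125.8 | 126 |
| Beta 0.1, neither halved | 1.960 + 1.282 | 101.7 | 102 |

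Only the last row agrees with the stated design. Its 102 is the normal approximation, and using the t-distribution raises it to the 103 of step 1. The 103 therefore came from the software, with the formula set beside it as a mis-typed illustration.

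**Step 3: which level do the documents state?** The sentence in section 3.4 says one-sided 2.5%. The software direction is one-sided and its alpha is 0.025. The output table repeats 0.025. Neither 2.24 nor 0.0125 appears in either document. The halved subscript is what one would write for a two-sided 5% test, where alpha/2 = 0.05/2 = 0.025 gives the same 1.960. The likely slip is that this subscript was kept while alpha was entered at its one-sided value.

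**Step 4: what the stricter cut-off would cost if someone used it.** At 0.0125 in one tail, power is 0.841 with 103 per group and 0.867 with 110, and 122 per group would be needed for 90%. These figures depend on a rule that the plan does not contain.

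**Step 5: the silence in SAP section 5.5.** An analyst who falls back on a conventional two-sided 5% test puts 2.5% in the upper tail. That is the same critical value as the stated one-sided 2.5% test: 1.960 on the normal scale, or about 1.97 for a t-test on 218 degrees of freedom (110 + 110 − 2). Either route gives the same decision about benefit.

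**The case for a change.** The strongest case for a change is that the contradiction is real and cheap to remove. Reaching 103 requires correcting three separate faults, so it is more than one stray subscript. The same text stands in both documents, and the surrounding definitions repeat the symbols, so damage in reading the PDF does not explain it. A reader who has only the Protocol sees no software output and cannot obtain 103 from the formula given there. And with the analysis sections silent, any doubt about the level falls on the primary outcome.

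The arithmetic part of this stands: the printed formula does not yield 103. The rest carries less weight. The Protocol reader still has the level, direction, power, SD and difference, and any standard calculation from those gives 102 or 103. The 0.9 is recognisable as the power, because the text and the software settings both give power as 90%. The two-threshold argument sets an inference from a subscript against a level stated in words and repeated in the software settings and output. The loss of power follows only if an analyst adopts that inference. A level and direction in SAP section 5.5 would be tidier, but the level is already stated in section 3.4, and the usual default leads to the same decision.

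**Conclusion.** The concern is right about the notation, but that does not reach the trial. The formula in Protocol section 9 and SAP section 3.4 is mis-typed and gives 55 or 147 depending on how beta is read. The sample size is correct for its stated inputs: 103 per group at one-sided 2.5%, with power 0.9009, rising to 0.919 at 110 per group. The level is stated consistently wherever it is stated outright, so the lower powers of 84.1% and 86.7% do not describe this plan. Correcting the symbols would leave the sample size, power, threshold and every result as they are. This is a clerical slip, together with a missing detail in SAP section 5.5 that an analyst would fill sensibly.

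The conclusion takes the SD of 2.2 and the difference of 1 as given, uses the equal-variance t-test on which the software run is based, and assumes no losses for the 0.919.

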**Design**

**Solve For:** Sample Size

**Test Direction**

Alternative Hypothesis: One-Sided

**Power and Alpha**

Power: 0.9

Alpha: 0.025

**Sample Size**

Group Allocation: Equal ( $N1 = N2$ )

**Effect Size**

Input Type: Difference

Difference in Means

$\delta$ : 1

Standard Deviation

$\sigma$ : 2.2

## Statistical Analysis Plan

PASS 2021, v21.0.3

### Two-Sample T-Tests Assuming Equal Variance

#### Numeric Results for an Equal-Variance T-Test

$$\delta = \mu_1 - \mu_2$$

Hypotheses:  $H_0: \delta \leq 0$  vs.  $H_1: \delta > 0$

Target Power	Actual Power	N1	N2	N	$\delta$	$\sigma$	Alpha
0.9	0.90089	103	103	206	1	2.2	0.025

**Figure 2.** Sample size calculation process

Finally, we decided to adopt a conservative approach and include 220 participants in this study. This study will take approximately three months to complete.

## 4 Investigational product

### 4.1 Name and description of investigational product(s)

Generative AI-Powered Puncture Surgery Navigation System for lung punctures (GPS-Lung) system.

### 4.2 Summary of findings from non-clinical studies

Although the algorithm has been developed to improve the quality of the CBCT images, no clinical studies have been published as yet.

### 4.3 Summary of findings from clinical studies

To date, no clinical studies have been performed, as only retrospective studies have been reported.

### 4.4 Summary of known and potential risks and benefits

Potential risks: During the procedure, it may not be possible to reconstruct the CBCT image into sCT image, resulting in the inability to use the sCT image for

## Statistical Analysis Plan

guided lung puncture procedures. In such cases, CBCT images could still be used to guide the puncture.

Potential benefits: Using GPS-Lung system for lung puncture guidance may reduce the puncture times, lower radiation dose and decrease complications of participants.

## 5 Statistical analysis

### 5.1 Withdrawal of individual subjects

Not applicable.

Patient data will be anonymized, and collected as part of standard practice of PLP. Therefore, participants cannot withdraw once data collection begins. Although the data will be anonymized, participants who object to the use of their data for research purposes (i.e., general ‘no-object’) will be excluded from the study.

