### **12.2 Informed consent**

All participants will be requested to sign an informed consent form prior to participation in the trial. The consent form will provide the participants with a clear explanation of the purpose of the study, potential risks, and possible benefits. Participants have the right to withdraw from the study at any time, without any impact on their subsequent treatment.

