### 5.3 Follow-up of subjects withdrawn from treatment

If participants refuse to undergo the 7-day postoperative complications follow-up, they will be excluded from this study.

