### 6.2 Recruitment and consent

Informed consent is required from all participants.

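### The protocol and SAP contradict each other on withdrawal, and SAP 5.3 drops randomised patients whose primary outcome is already recorded

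*SAP*

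**What the plan says.** Four rules bear on a participant who wants to leave.

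- Protocol 12.2 (Informed consent): "Participants have the right to withdraw from the study at any time, without any impact on their subsequent treatment".
- SAP 5.1 (Withdrawal of individual subjects): the section is headed as not applicable, gives anonymised, routinely collected data as the reason, and concludes that "participants cannot withdraw once data collection begins".
- SAP 5.1, next sentence: despite the anonymisation, "participants who object to the use of their data for research purposes" are to be excluded from the study. No time point is given.
- SAP 5.3 (Follow-up of subjects withdrawn from treatment): "If participants refuse to undergo the 7-day postoperative complications follow-up, they will be excluded from this study".

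The context is as follows. SAP 3.1 states that "Participants will be randomized before PLP initiation". SAP 6.2 states that "Informed consent is required from all participants", and SAP 3.2 already makes refusal of consent an exclusion criterion. SAP 5.2 rules out replacement. SAP 5.4 expects no missing data and gives no method for handling any. Neither document defines an analysis set or says whether data gathered before a withdrawal are kept.

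**The concern.** A participant who asks to leave during the trial is entitled to do so under the protocol and is refused under the SAP. Site staff and the statistician cannot comply with both.

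The statistical consequence follows from the gap. If the protocol right is honoured, the SAP has no way to handle the person's data except removal, which is what SAP 5.3 prescribes for those who decline follow-up. The primary outcome, radiation dose and duration of surgery are all known when the procedure ends, so declining a later complication check is no reason to discard them. By then the patient has experienced the procedure, and the doctors, technicians and nurses know both how it went and the arm. If the decision to decline is related to a difficult procedure, the patients removed will tend to have high puncture counts, and the comparison of those who remain is no longer protected by randomisation.

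**Working it through.** **1. The rules side by side**

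| Situation | Protocol 12.2 | SAP 5.1 | SAP 5.3 |
|---|---|---|---|
| Asks to leave after data collection starts | Allowed | Not possible | No rule |
| Objects to research use of data | Not addressed | Excluded, time not stated | No rule |
| Declines the 7-day follow-up | Allowed, as part of leaving at any time | Not possible, if this counts as withdrawal | Excluded |

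The first row is a direct contradiction. SAP 5.1 also conflicts with itself, because it says nobody can leave and then excludes objectors.

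**2. Which removals certainly fall after randomisation**

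Randomisation comes before the puncture (SAP 3.1) and the 7-day check comes after it. Under SAP 5.3, therefore, a patient who declines the check once the procedure is over is removed with the arm assigned and the puncture count, dose and duration recorded. For objectors the SAP gives no timing, so the same cannot be said with certainty.

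**3. The plan's own sample size**

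Inputs (SAP 3.4): difference 1, SD 2.2, one-sided alpha 0.025, target power 90%. An equal-variance two-sample t-test (noncentral t) with 103 per group gives power 0.9009, which matches the 0.90089 in the software output.

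**4. Loss of power from removals**

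The margin is 220 − 206 = 14 participants, or 7 per group (7/110 = 6.4%). With equal removal from both arms:

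| Per group | Removed | Power |
|---|---|---|
| 110 | 0% | 0.919 |
| 103 | 6.4% | 0.901 |
| 99 | 10% | 0.889 |

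The documents give no removal rate, so these percentages are assumptions.

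**5. Bias from selective removal (illustration)**

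Assume that a fraction f = 0.05 of the GPS-Lung arm is removed, that those removed average d = 2.2 punctures (one SD) more than those retained, that nobody is removed from control, and that there is no true difference.

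- Mean of the whole arm = retained mean + f × d, so the retained mean is too low by 0.05 × 2.2 = 0.11 punctures.
- Retained n = 110 × 0.95 = 104.5. SE = 2.2 × √(1/104.5 + 1/110) = 0.30.
- Shift in SE units = 0.11/0.30 = 0.37.
- One-sided rejection = 1 − Φ(1.96 − 0.37) = about 5.5%, against the nominal 2.5%.
- If the same removal is from control, the shift is 0.11 against GPS-Lung and the one-sided rejection is 1 − Φ(1.96 + 0.37) = about 1.0%.
- If there is no true effect and removal works identically in both arms, the two shifts cancel.

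**The case against.** The strongest defence reads SAP 5.1 narrowly. The sentence follows from a remark about anonymised data, so it may mean only that data already collected cannot be retracted, while Protocol 12.2 concerns continued participation. The consent form is not among the pages available for this review, so its own terms on data already collected cannot be checked. This reading would be close to the rule proposed here. It fails on the text: the SAP speaks of participants, not data, and its next sentence excludes objectors although the data are anonymised, so anonymisation is not treated as making removal impossible.

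Three other points on that side stand.

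- A reader might infer that SAP 5.1 removes objectors after randomisation. The documents do not say so. The clause could refer to a standing objection known before enrolment. Its place under withdrawal, and the fact that "Participants are unwilling or unable to sign informed consent" is already an exclusion criterion, suggest a later action, but that is inference. The firm evidence of post-randomisation removal is SAP 5.3 taken with SAP 3.1.
- A reader might infer that removals seriously threaten power. They do not at the rates shown: even 10% removal leaves 0.889.
- Participants are to be blinded, and the staff who know the arm are kept out of data collection and analysis (Protocol 6.2, SAP 3.3). This limits the routes by which removal could differ by arm. It does not close them, because those staff still treat the patient, and patients can react to how the procedure went without knowing their arm.

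**Conclusion.** The contradiction between Protocol 12.2 and SAP 5.1 is explicit and depends on no figure. The exclusion in SAP 5.3 is a separate defect in the analysis: it discards recorded primary-outcome data from randomised patients for a reason that arises afterwards. Both should be corrected.

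The size is conditional. The shift of 0.11 punctures, against a design difference of 1, and the error of about 5.5% rest on an assumed 5% removal from the GPS-Lung arm only and an assumed gap of one SD. A reader might take them as a forecast, or conclude that the rule necessarily favours the new system. Neither is supported: the documents give no removal rate, and the direction depends on which arm loses patients. The sample size itself is not in error on this point.

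**What to change.** Reconcile SAP 5.1 to 5.3 with Protocol 12.2 so that both documents state one withdrawal right. Replace the sentence in SAP 5.1 that denies withdrawal, and the exclusion in SAP 5.3, with a rule to this effect:

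- All randomised participants are analysed in the arm to which they were assigned.
- Data collected up to withdrawal are kept unless the participant withdraws consent to their use.
- Participants who decline the 7-day follow-up stay in the analyses of puncture count, radiation dose and duration of surgery, and are missing only for later complications. SAP 5.4 should acknowledge this missing information.
- Exclusion for objecting to research use of data applies only to objections made before randomisation. A later objection is handled as withdrawal of consent to data use.
- Withdrawals, and any removal of data at a participant's request, are counted and reported by arm.

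The wording on data retention should be checked against the signed consent form. The cost is a short amendment, submitted to the ethics committee by the route in SAP section 8. It needs no extra patients, procedures or data collection.
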